 - 1. 100 clinical trial participants, 30-60 typically-developing reference controls,
 - 2. 200 total clinical trial participants, 30-60 typically-developing reference controls,

We will have 200 people with Down syndrome taking placebo or medication.

100 will be locally recruited, 100 will be recruited in Brazil. 30-60 out of the 100 recruited locally (with Down syndrome, taking study medication) will also take part in the MRI substudy.

We will have an additional 30-60 control participants recruited locally for just the MRI/EEG substudy (no medication, medical visits or neuropsychological testing)

Vulnerable Populations

- 1. Indicate specifically if you will include each of the following special populations by checking the appropriate box:
 - **⊠** Adults unable to consent

\boxtimes	Minors (infants, children, teenagers)
	☐ Wards of the state
	☐ Foster Children
	Pregnant Women
	Neonates
	Neonates of Uncertain Viability
	Employees of CWRU or UHHS
	Prisoners
	Illiterate Individuals
\boxtimes	Non-English Speaking
	University Students

2. If the research involves individuals that are included in a vulnerable population, describe the additional safeguards included to protect the rights and welfare of the individuals for each population indicated.

It is the responsibility of the investigators to obtain written informed consent from each caregiver and subject (or her/his legal representative, if the subject is not capable of giving written informed consent and the caregiver is not her/his legal representative) participating in this study, after providing a clear explanation of the methods, objectives and potential hazards of the study at a appropriate terms for the comprehension level of the subject, authorized representative, and caregiver (who can be the same person as the authorized representative). In the case of subjects with Down syndrome not legally responsible for themselves, consent will be obtained from their legal authorized representative. Even when the subject is not fully capable of giving written informed consent, the subject must assent in writing to participation in the study (this is in addition to obtaining informed consent from her/his legal representative).

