- 2. Prospective subjects and/or caregivers must express interest in learning more about the study and give their contact information to the investigators before investigators will contact them. No "cold-calling" will occur.
 - All prospective subjects with Down syndrome and/or their caregiver will be informally prescreened by telephone to assess probable eligibility for the study. The telephone prescreening questions for will consist of five questions: 1) confirmed diagnosis for Down syndrome? 2) Can the person communicate verbally? 3) What is the person's gender?; 4) What is the person's age?; 5) Is the person taking any new medication or is on a new dose for thyroid medication or for diabetes? At this time, the requirements of the protocol will also be explained briefly to avoid the time and expense of bringing candidates who are unlikely to comply with the requirements of the study to the study site for further evaluation. Provided they meet the prescreening requirements, potential participants and caregivers who appear suitable for the study will be scheduled for a screening visit.
- 3. The prevalence of Down syndrome in the general population is 1 in 1000. From the data available, we know that this genetic disorder affects both genders and different ethnic groups equally. During recruitment, we will attempt to involve an equal number of female and male participants. Also, the P.I. will make every effort to include subjects belonging to minority ethnic groups in this study. Given that Brazilians are defined as Hispanic/Latino, according to the National Institutes of Health, we will have a significant number (at least 50%) of participants belonging to this particular ethnic minority group.
- 4. For the Cleveland site of this study, a total of 100 persons with Down syndrome from both genders and between the ages of 15 and 32 will be recruited in conjunction with the regional parent associations (such as the The Up Side of Downs in Cleveland and the Down Syndrome Association of Central Ohio in Columbus), local and regional clinics as well as County Boards of Developmental Disabilities will also be contacted. Depending on the success of (or lack of success of) this traditional approach, we also plan to make use of the online recruiting tools ResearchMatch and DS-ConnectTM: The Down

HRP-503BIO	TEMPLATE: Biomedical Protocol				
Approved:	05/11/2018	Prior Version:	1/23/2018		

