Syndrome Registry. Of these 100 participants, 50 participants will be assigned to be treated with memantine and 50 age- and gender-matched participants will be assigned to the placebo arm of the study. The Up Side of Downs in Cleveland and the Down Syndrome Association of Central Ohio in Columbus have expressed great enthusiasm for this project, and plan to use their membership databases to contact potential subjects for this study. For the majority of participants to be enrolled, all the testing (neuropsychological, medical, clinical laboratory, and electrophysiological tests) will be carried out at University Hospitals. For a subset of 30-60 participants, magnetic resonance imaging (MRI) of the brain will be performed at the Cleveland Clinic.

In addition, we also expect to recruit 30-60 participants without Down syndrome as typically-developing reference controls in the Cleveland site for the magnetic resonance imaging (MRI) assessments. From previous experience, recruiting typically-developing participants for a study involving persons with Down syndrome, we expect to recruit these age and gender matching control participants from the family and friends of the participants with Down syndrome. In case it proves necessary, we may also use ResearchMatch and posting at Case Western Reserve University to recruit this cohort of control, typically-developing participants.

The São Paulo, Brazilian arm of this study will comprise 100 participants with Down syndrome to be recruited through local parent associations and from Drs. [name] or [name]'s patient database. ([name] runs a large Down syndrome Clinic in the city of São Paulo and will function as a consultant for this study.) [name] [name] will be responsible for translating this protocol into Portuguese in consultation with [name] and make the necessary adjustments to comply with Brazilian federal and state laws and regulations.

5. Materials used to recruit research participants include an advertisement. A poster consisting of pictures of a participant doing some tasks in the clinical trial is used as visual aid during informed consent.

Setting

- 1. Describe the sites or locations where your research team will conduct the research. The study will be conducted at Case Western Reserve University and University Hospitals, Cleveland Ohio, USA (100 subjects), and Hospital Israelita Albert Einstein (English: Albert Einstein Israelite Hospital) in São Paulo, Brazil (100 subjects).

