The sample size for this project was calculated from power analyses performed on the data from our pilot study (Boada et al., 2012; APPENDIX 6). One hundred (100) subjects per treatment group will provide approximately 99.9% power to detect a between-group mean difference of 4 points on the California Verbal Learning Test II short form (CVLT-II short form) with respect to change from baseline to week 16 endpoint with a one-tail, paired design, and an alpha = 0.025. These calculations were performed using the PASS 12 software (Version 12.0.3; NCSS, LLC. Kaysville, Utah, USA. www.ncss.com). Sixty (60) subjects per treatment group (the Cleveland site) are already expected to produce approximately 99% conditional probability of rejecting the null hypothesis. Therefore, in case any unanticipated (technical or regulatory) issues happen to impede or delay the performance of the trial in the São Paulo site, the Cleveland site should provide enough power to confirm or reject our previous observations in the pilot

HRP-503BIO	HRP-503BIO TEMPLATE: Biomedical Protocol			
Approved:	05/11/2018	Prior Version:	1/23/2018	

study. Obviously, the larger the study, the greater the conditional probability of rejecting the null hypothesis, therefore, our intent is to combine the data from both sites into one large dataset.

Randomization Method

A computer generated, blinded randomization list will be used. Subjects will be paired according to age and gender. At the baseline visit subjects will be assigned to one of the two treatment regimens (memantine or placebo). The random code will assign subjects to treatments in a 1:1 ratio.

Replacement Policy for Subjects Withdrawn from the Study

To minimize missing data points in this paired-design study, replacement of an individual in memantine/placebo age-gender matched pairs will be acceptable until such subject complete the 16 weeks on the study medication; a special age-gender matching code will be created for the replacement subject to indicate that he/she has replaced one of the subject in a memantine/placebo pair. Data on any adverse event that may have caused the subject to drop from the study will be recorded and reported in the manuscript describing the study findings. After the subject start taking the study medication, if the subject drops from the study due to a severe adverse event, he/she will not be replaced.

Study Populations

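### The Cleveland-only power of about 99% is quoted for 60 per group, but Cleveland is planned at 50 per group, where the protocol's own figures imply about 94% to 97%

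*Combined protocol and SAP*

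**What the plan says.** The Sample Size section (Data Analysis Plan) gives two power statements. For the full trial: "One hundred (100) subjects per treatment group will provide approximately 99.9% power to detect a between-group mean difference of 4 points", for change from baseline to week 16, one-tailed, paired design, alpha 0.025. For Cleveland alone: "Sixty (60) subjects per treatment group (the Cleveland site) are already expected to produce approximately 99% conditional probability of rejecting the null hypothesis". The next sentence draws the consequence: if technical or regulatory problems hold up São Paulo, Cleveland by itself has the power to confirm or reject the pilot finding.

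The planned site sizes appear in several other places:

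- Number of Research Participants: "200 total clinical trial participants", and "100 will be locally recruited, 100 will be recruited in Brazil".
- Recruitment Methods, item 4: "For the Cleveland site of this study, a total of 100 persons with Down syndrome", and then "Of these 100 participants, 50 participants will be assigned to be treated with memantine and 50 age- and gender-matched participants will be assigned" to placebo.
- Recruitment Methods, item 4, on São Paulo: "Brazilian arm of this study will comprise 100 participants with Down syndrome".
- Setting: 100 subjects at each of the two sites.

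The Randomization Method section specifies 1:1 allocation, which agrees with 50 and 50.

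**The concern.** The Cleveland-only sentence attaches a sample size to a named site, and no other part of the protocol plans that size there. The only other place a 60 occurs is in the ranges of 30 to 60 for the MRI subset and for the untreated reference controls. Neither is a trial arm.

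The sentence supports the protocol's stated contingency. If São Paulo stalled, the team could not tell from the protocol whether Cleveland should stop at 100 or at 120. If it stopped at 100, the quoted power would belong to a trial with 20 more subjects.

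**Working it through.** **1. Head count.** As the Sample Size section has it: 2 × 60 = 120 at Cleveland, and 120 + 100 in São Paulo = 220. As the rest of the protocol has it: 2 × 50 = 100, and 100 + 100 = 200. Only the second matches the planned total.

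**2. Inputs for power.** From the Sample Size section: difference Δ = 4 points, paired design, one-sided α = 0.025, stated power 99% at 60 per group and 99.9% at 100 per group. The section prints no standard deviation (SD) and no correlation, so the SD of the within-pair difference, σ, is solved from each stated power. I read the phrase about the conditional probability of rejecting the null hypothesis as power; the paragraph itself goes on to conclude that there is enough power.

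**3. Formula.** With n pairs and d = Δ/σ, power = P(T > t₀.₉₇₅,ₙ₋₁), where T is noncentral t with n − 1 degrees of freedom and noncentrality d√n.

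**4. Do the two stated powers agree with each other?**

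| Anchor | d | σ = 4/d | Power at 50 | Power at 60 | Power at 100 |
|---|---|---|---|---|---|
| 99% at 60 | 0.563 | 7.11 | **97.4%** | 99.0% | 99.98% |
| 99.9% at 100 | 0.510 | 7.84 | **94.2%** | 97.3% | 99.9% |

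Each anchor reproduces the other stated power to within 2 percentage points, so the two are roughly consistent. They do not share one exact σ.

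**5. Power at the planned 50 per group.**

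- First anchor: noncentrality 0.563 × √50 = 3.98, critical value 2.010, power 97.4%.
- Second anchor: noncentrality 0.510 × √50 = 3.61, same critical value, power 94.2%.

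The chance of missing the effect is therefore 2.6% to 5.8%, against the 1% implied by the text. The shortfall from the stated 99% is 1.6 to 4.8 points.

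**6. Rounding of the stated powers.**

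- 98.5% to 99.5% at 60 gives σ from 7.38 down to 6.72, and 96.4% to 98.5% at 50.
- 99.85% to 99.95% at 100 gives σ from 8.04 down to 7.54, and 93.2% to 95.7% at 50.

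The overall range at 50 is 93.2% to 98.5%.

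**7. Sensitivity.** An unpaired t test with 2n − 2 degrees of freedom gives 97.4% and 94.4% at 50 per arm. The result depends only on d. If the 99% was computed for a difference other than 4 points, 97.4% still holds, for that other difference.

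**8. Size needed for 99%.** 60 pairs at σ = 7.11; 73 pairs at σ = 7.84.

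**The case against.** The count mismatch has no good answer, but the power figures can be challenged on four grounds.

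- **The two anchors do not share one SD.** Even with rounding, the SD bands (6.72 to 7.38 and 7.54 to 8.04) do not overlap. With the SD behind 94.2%, power is already only 97.3% at 60, so part of the gap from 99% has nothing to do with 50 versus 60. This stands. The size error alone costs 99.0 − 97.4 = 1.6 points on one anchor and 97.3 − 94.2 = 3.1 points on the other.
- **A power of 99.9% is a weak anchor,** because small changes near the ceiling move the SD a good deal. If the software gave 99.98% and this was truncated, the SD is about 7.2 and power at 50 is 97.1%. That is possible. It pulls the estimate towards the upper end but not up to 99%.
- **The top of the rounding range, 98.5%, might loosely be called about 99%.** True. What is certain is that the count is wrong; that the power is overstated is probable, and the amount is small.
- **The real inputs are not visible.** The section cites the pilot data in Appendix 6, which was filed separately, so a back-solved SD is no substitute for a rerun. This stands, and the rerun could land well below 94%. Assume pilot arms of 18 (the memantine denominator in the risk section) and 19 (37 completers − 18). The printed standard errors then give visit SDs of about 7.1 to 8.9. With independent pair members, power at 50 pairs runs from about 55% at a baseline-to-week-16 correlation of 0.3 to 97% at 0.8. That is a separate question about the inputs, but it is a reason not to treat 94% to 97% as final.

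It is also fair to say that the sentence supports only a fallback. The stated intent is to pool both sites.

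**Conclusion.** The concern holds. The Sample Size section gives Cleveland 60 per group, while every other statement of the site's size gives 100 participants, and the one that states a split gives 50 and 50. That conflict needs no assumption.

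On the protocol's own stated powers, Cleveland alone at the planned size has about 94% to 97% power, not 99%. Allowing for rounding it is 93.2% to 98.5%, below 99% on every anchor tried. This rests on an SD solved from the stated powers and on reading the quoted probability as power.

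The practical effect is modest. On these figures the fallback keeps more than 90% power, so its conclusion is not overturned, and the 100-per-group calculation is not in dispute here. It should be corrected because a stated contingency rests on a sample size that the plan does not contain.

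**What to change.** Reconcile the Cleveland number in the Sample Size section with Number of Research Participants, Recruitment Methods and Setting. On the current plan it is 50 per group. If 60 per group is intended, the Cleveland target of 100 and the total of 200 must change instead.

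Then rerun the Cleveland-only power at the reconciled size from the pilot inputs actually used, and replace the 99% with that result. Print beside it the SD of the pair difference (or of change) and any correlation assumed. The 94% to 97% above shows what to expect at 50 per group if the stated powers are sound; the rerun value is the one to publish.

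The cost is one corrected sentence and one run of the power software. If 50 per group stands, enrolment, randomisation and endpoint do not change. The only downside is a somewhat less favourable power for the fallback.

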Once again, at the end of this visit, the subject will be asked to go to Investigational Drug Services (IDS) at University Hospitals in the Cleveland site where a study coordinator will dispense a 66-day supply (56 days plus 10 extra days) of either memantine capsules or identically-looking placebo capsules. For the 16-week duration of this study, capsules will be taken either once (first week) or twice daily (weeks 2-16) by mouth according to memantine's standard titration schedule. In the São Paulo site, a physician at the Hospital Israelita Albert Einstein (English: Albert Einstein Israelite Hospital)s will provide a 60-day supply of either memantine capsules or identically-looking placebo capsules, which will come randomized and prepackaged from the University of Iowa Pharmaceuticals Services.

Visits 4: Primary and Secondary Efficacy Measures at the 16th week from the start of the medication. Various aspects of the subjects' learning, memory, cognition, and adaptive behavior will be assessed again through the same neuropsychological test battery used in visit 2. Again, we expect that the test battery will take approximately two hours to administer. Therefore, two visits may be required to complete this series of assessments for a few participants. Again, for a subset of 30-60 participants in the Cleveland site, magnetic resonance imaging (MRI) of the brain will be performed at the Cleveland Clinic in the afternoon, one or two hours after the completion of the neuropsychological test battery.

Visit 5: Second and final follow-up medical visit at the 16th week from the start of the medication. The purpose of this visit is to ensure again that the study medication is being adequately tolerated. Similarly to visits 1 and 3, vital signs will be measured and a physical examination will be performed. Two blood samples again will be collected for checkup tests (here, the second blood sample is not optional!). In addition, a quantitative assessment of steady-state plasma levels of memantine and Alzheimer's disease biomarkers will be performed in the end of the study, after the unblinding of the randomization codes. The general procedures to be followed in this visit are listed below:

- Vital Signs
- Adverse Event Assessment
- Medication Compliance Check
- Complete Physical Exam
- Neurological Exam
- The Screen for Childhood Anxiety Related Emotional Disorders (SCARED)
- Concomitant Medication Check

HRP-503BIO	TEMPLATE: Biom	edical Protocol	

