Approved:	05/11/2018	Prior Version:	1/23/2018

- 12-lead ECG
- Labs (including urine pregnancy test for females of childbearing potential)

Again, in the Cleveland site, [name] will perform the electrophysiological assessments of auditory evoked potentials (Auditory Brainstem Response, ABR, Test and Mismatch negativity, MMN) shortly after this visit is completed. (His Research Assistant and one of the Study Coordinators, [name], may also perform some of these assessments under [name] supervision.) In the São Paulo site, these assessments will be carried out by [name], M.S., and may require the Brazilian participants to come for an additional visit.

If for some reason the subject withdraws from this study prior to Visit 5, he/she will be asked to return to the clinic for a "Treatment Discontinuation Visit." In addition, if the subject discontinues the medication prior to the end of the study, he/she will be asked to complete a "Retrieved Dropout Visit" on the date that should have represented Visit 5. Study medication will not be provided beyond the study period. The procedures for the "Treatment Discontinuation Visit" will be the same as those described for "Visit 5 (Second follow-up medical visit)."

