An "intention-to-treat" approach will be used in the statistical analyses, so that data from all subjects will be included regardless of subject eligibility or adherence to the protocol. The intent-to-treat (ITT) population is defined as all subjects who received at least one dose of medication and at least one evaluation at the start of double-blind treatment irrespective of compliance and protocol violations.

An "efficacy evaluable" population will be determined based on blinded application of protocol criteria, and a statistical assessment of this group will also be performed, and 80% or greater medication compliance and no major protocol violations will be required for a subject to be "efficacy evaluable." Repeated measures mixed models (MIXED) from SPSS will be used to deal with missed data.

Demographics and Baseline Characteristics

Demographic and baseline characteristics will be summarized by treatment, and simple comparisons of the mean numerical values of these characteristics between memantine and placebo groups will be performed using the two-tailed unpaired t test. Comparability of treatment groups at baseline will be tested for the efficacy parameters in the analysis of efficacy.

Efficacy Parameters

The two primary efficacy endpoints are the comparison of the effects of memantine and placebo on the California Verbal Learning Test II short form (CVLT-II short form). The CVLT-II short form score range is 0 to 36; the baseline and post-intervention scores of the participants

HRP-503BIO	503BIO TEMPLATE: Biomedical Protocol			
Approved:	05/11/2018	Prior Version:	1/23/2018	

with Down syndrome in our pilot study (Boada et al., 2012; APPENDIX 6) were 14.53 ± 1.80 and 20.12 ± 2.10 (mean \pm SEM), for the memantine arm, compared to 16.26 ± 1.82 and 13.74 ± 1.63 , for the placebo arm of the trial. (Higher score indicates better performance.) This measure is dependent on the functional integrity of temporal lobe structures such as the hippocampus. Improvement in performance in this measure is expected to be correlated to improvements in the individuals' ability to acquire skills requiring the use of declarative memory. Ultimately, in case we are able to confirm that the administration of memantine is indeed efficacious in improving this cognitive measure in this population, such gains may lead to a measurable improvement in the quality of life of persons with Down syndrome.

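### No dropout visit is stated to include the CVLT-II, so early leavers have no week-16 primary score, and replacing them fills a place without recovering that score

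*Combined protocol and SAP*

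**What the plan says.** **When the primary measure is collected.** Under Study Design, Procedures and Timeline, the CVLT-II is part of the Visit 2 battery. At Visit 4 subjects "will be assessed again through the same neuropsychological test battery used in visit 2". Table 1 marks the CVLT-II at Visits 2 and 4 and nowhere else. Visit 5 is a medical visit; its procedures do not include the CVLT-II.

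**What happens when someone leaves.** The same section, and again Withdrawal of Research Participants, provide two visits. The procedures of the Treatment Discontinuation Visit "will be the same as those described for" Visit 5. The Retrieved Dropout Visit, for subjects who stop medication early, takes place "on the date that should have represented Visit 5". Its procedures are not listed, and it has no column in Table 1.

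**How missing data are handled.** Replacement Policy for Subjects Withdrawn from the Study aims to keep missing data points few. It says that "replacement of an individual in memantine/placebo age-gender matched pairs will be acceptable until such subject complete the 16 weeks on the study medication", and that "a special age-gender matching code will be created for the replacement subject". There is one exception: after dosing, "if the subject drops from the study due to a severe adverse event, he/she will not be replaced".

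**How the data are analysed.** Study Populations promises an intention-to-treat approach that uses data from all subjects. It defines that population as "all subjects who received at least one dose of medication and at least one evaluation at the start of double-blind treatment", and relies on SPSS MIXED for missing data. Statistical Models takes change from baseline as the dependent variable, with treatment, baseline and, if significant, their interaction.

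**The concern.** The analysis promise and the visit schedule do not meet. There is only one post-baseline CVLT-II, at week 16. A subject who leaves before Visit 4 has no change score unless one of the dropout visits supplies it, and neither is stated to do so. MIXED cannot repair this: with change as the outcome and a single post-baseline measurement, such a subject contributes no outcome. If the two raw scores were modelled instead, the missing one could be recovered only through baseline.

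The replacement rule addresses the number of subjects, not the lost information. A new subject's score says nothing about what the person who left would have scored at week 16. In effect the primary comparison becomes one of completers. Completers can differ between arms for reasons unrelated to the drug's effect on memory, because some withdrawals are tied to tolerability: the plan withdraws subjects who fail re-challenge and those with a serious adverse event. At stake are a shift in the estimated difference and a one-sided 2.5% error rate that is no longer 2.5%.

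**Working it through.** **Power is not the issue.** The plan states about 99.9% power for 4 points with 100 per arm (one-sided 0.025, paired). No SD of change or of pair differences is given, so this figure cannot be reproduced from stated inputs. Solving backwards, the pair-difference SD would be 4 × √100 / (1.960 + 3.090) = 7.92. At the pilot's 7.5% dropout without replacement, 100 × 0.925² ≈ 86 intact pairs remain. At SD 7.92, power with 85 pairs is still 99.6%. Larger SDs would cost more, but the main question is bias.

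**Inputs**
- Dropout: 37 of 40 pilot subjects completed (Background, pilot trial), so 3/40 = 7.5%, exact 95% CI 1.6% to 20.4%. Of 200 subjects that is about 15 (3 to 41). No rates by arm are given.
- SD: pilot SEMs (Efficacy Parameters) times √n, with n = 18 on memantine (Risks) and 19 on placebo (assumed, 37 − 18). At baseline, 1.80 × √18 = 7.64 and 1.82 × √19 = 7.93. I take 7.8 at both times.
- Assumed baseline-to-week-16 correlation: 0.6. Residual SD = 7.8 × √(1 − 0.36) = 6.24; SD of change = 7.8 × √(2 × 0.4) = 6.98.
- Assumed: no drug effect, and dropouts who would have scored d = 0.5 to 1 residual SD below what baseline predicts.

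**Bias among completers, adjusted for baseline**

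bias = d × 6.24 × [p₁/(1 − p₁) − p₀/(1 − p₀)], where p₁ is memantine and p₀ placebo dropout.

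At 10% vs 5%: 0.10/0.90 − 0.05/0.95 = 0.1111 − 0.0526 = 0.0585. Bias = 0.5 × 6.24 × 0.0585 = 0.18, up to 1 × 6.24 × 0.0585 = 0.36. That is 5% to 9% of the 4-point target.

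**Error rate.** With 100 completers per arm the standard error is 6.24 × √(2/100) = 0.88. The rejection probability under no effect is P(Z > 1.96 − 0.18/0.88) ≈ 4.0%, up to P(Z > 1.96 − 0.36/0.88) ≈ 6.1%. With the rates reversed it is about 1.5% down to 0.9%.

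**Simulation** (20,000 trials per scenario, baseline-adjusted, same assumptions):

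| Dropout, memantine vs placebo | Handling | Bias (points) | One-sided error |
|---|---|---|---|
| 10% vs 5% | replaced in the same arm until 100 complete | +0.18 to +0.36 | 3.8–6.4% |
| 10% vs 5% | not replaced, scores missing | +0.18 to +0.36 | 3.8–6.1% |
| 10% vs 5% | half of the scores retrieved | +0.09 to +0.16 | 3.1–3.8% |
| 10% vs 5% | all scores retrieved, with or without replacement | 0.0 | 2.5–2.6% |
| 5% vs 10% | scores missing | −0.18 to −0.36 | 0.9–1.6% |
| 7.5% vs 7.5% | scores missing | none | 2.4–2.7% |
| 15% vs 5% | scores missing | +0.38 to +0.77 | 6.2–14.4% |

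If dropout depends on baseline only, the adjusted bias is 0.0 and the error 2.4–2.6% in all scenarios.

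The first two rows isolate replacement: it changes almost nothing. The fourth row isolates retrieval: it removes the bias whether or not anyone is replaced. The simulation replaces every dropout, which overstates what the plan allows.

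**The case against.** **The scores may not be lost.** The Retrieved Dropout Visit is separate from the Treatment Discontinuation Visit and falls at week 16. Nothing says that a subject who only stops medication skips Visit 4, and the case report form, a separate appendix, may list the visit's content. This stands to the extent that one can say only that collection is not stated, not that it is excluded. It does not answer the gap: the protocol text and Table 1 should fix when the primary endpoint is measured.

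**The bias rests on assumptions.** This also stands. No rates by arm are given, and the Risks section reports equal discontinuation for adverse events in dementia trials. The 10% vs 5% and 15% vs 5% splits and the 0.5 to 1 SD deficit are illustrations; the 15% vs 5% row is an extreme.

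**Stronger readings that the documents do not support**
- A reader might infer that replacement itself biases the trial. The comparison above shows almost no added harm. Even with same-arm replacement of all dropouts at 10% vs 5%, memantine would be about 111 of 216 dosed (51%).
- A reader might infer that the newcomer simply takes the vacated arm. The plan is silent on this. Assignment follows a computer-generated schedule, "A computer generated, blinded randomization list will be used", and replacements are not exempted. Nor is there any stated route to unblinding.
- A reader might infer that replacement restores 100 per arm. It is optional and excludes dosed subjects lost to a severe adverse event, who are neither replaced nor stated to be scored.
- A reader might infer that the ITT set is ambiguous. Its definition admits both the person replaced and the replacement. How a replacement is assigned, and how a replaced pair is reported, needs only a minor clarification.

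**Conclusion.** The concern holds for the missing scores. As written, a subject who leaves before Visit 4 has no stated week-16 CVLT-II and drops out of the primary analysis, which contradicts the promise to use data from all subjects. Replacement does not mend this and does not cause it.

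The consequence is conditional and modest. Bias needs dropout that is both unequal between arms and related to outcome beyond baseline. Under the assumed 10% vs 5% split it is 0.18 to 0.36 points. If dropouts do worse than predicted, it favours memantine when memantine loses more (error about 4–6%) and goes against it when placebo loses more (about 1–1.6%). With equal dropout, or dropout that depends on baseline only, it is zero. The documents do not show which case applies. The point is worth acting on because the primary endpoint is exposed and the remedy is cheap. The calculations do not support a ban on replacement after dosing.

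**What to change.** 1. List the CVLT-II among the procedures of the Retrieved Dropout Visit, which is already planned for week 16, and add that visit to Table 1.
2. State that these scores enter the ITT analysis, and that every dosed subject stays in the assigned arm whether or not a replacement is enrolled.
3. As a minor clarification, say how a replacement's treatment is assigned and how a pair with a replaced member is reported.

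The cost is wording plus one CVLT-II for about 15 people (200 × 3/40; 3 to 41 over the pilot's confidence interval). Some will decline, so the bias is reduced rather than surely removed: in the 10% vs 5% case, retrieving half of the scores brings it to 0.09 to 0.16 points and the error to 3.1–3.8%. No change to treatment or to the withdrawal rules is involved.
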